3. STUDY POPULATION

#UTHealth Houston IRB NUMBER: HSC-MS-22-0689
IRB APPROVAL DATE: 01/05/2024

All patients admitted to the medical ICU of Memorial Hermann Cypress and to the medical ICU of Memorial Hermann at the Texas medical Center will be screened for eligibility. There will be no restrictions based on the race of subjects. The study will not involve children as the investigators are only credentialed to treat adults aged 18 years and older.

3.2. Criteria for Recruitment

Patient will be screened to confirm they meet study criteria. Consent will be obtained from the legal authorized representative.

3.3. Inclusion Criteria

Patients will be enrolled only if they consented and they meet all of the inclusion criteria listed below.

- 1. Patients 18 years or older
- 2. Patients on IMV for more than 72 hours
- 3. Patients infused Fentanyl or Hydromorphone for more than 72 hours
- 4. Patients with evidence of reversal of process that caused respiratory failure, adequate oxygenation (PaO2/FIO2>200; Positive end expiratory pressure (PEEP)≤8 and Ph≥7.2
- 5. Patients hemodynamically stable
- 6. Patients with a failed single or multiple attempts at spontaneous breathing trials

3.4. Exclusion Criteria

All subjects meeting any of the exclusion criteria at baseline will be excluded from participation.

- 1. Patients with history of opioid drug abuse
- 2. Patients receiving schedule II narcotics on a chronic basis for longer than 6 months prior to ICU admission or on other analgesic infusions other than Fentanyl or Hydromorphone
- 3. Patients with cervical spinal cord injury or neuromuscular disease
- 4. Patients with end stage liver disease at ICU admission (ie, International normalized ratio ≥2and not taking warfarin and/or a total serum bilirubin ≥1.5 times above normal limits
- 5. Patients with prolonged QTc interval ≥500
- 6. Patients with prior history of cardiac conduction defects or suddendeath
- 7. Patients with QTc increase of ≥60 milliseconds above the value of prior EKGs measured during current ICU admission
- 8. Patients with more than 5 days on IV analgesia
- 9. Patients intubated for more than 30 days
- 10. Patients without feeding tubes
- 11. Patients not receiving enteral feeding
- 12. Exclusion of patients in a comatose state
- 13. Exclusion of patients in Status Epilepticus
- 14. Exclusion of post-operative patients

3.5. Withdrawal Criteria

The study will be discontinued after completion or upon recommendation from Data Safety and Monitoring board DSMB and with help from IRB.

3.6. Subject Replacement

Yes, Subjects who drop out will be replaced.

#UTHealth Houston

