2.5 Outcomes

a. Primary

Proportion of patients on methadone that get extubated by day number 5 from the date of intubation

b. Secondary

Proportion of patients that develop prolonged QTC after administration of methadone. Others will be ICU length of stay, ICU mortality, hospital length of stay and hospital mortality.

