4.2 Interventions

Pre-intervention period (1 month)

The objective of this period is to standardize the process to improve familiarity to the investigators. Study procedures will be presented to the nurses by oral presentations, printed material, and by email. The information will include detailed explanation of the process of tapering methadone and weaning patients off opiates as stipulated in the study. It will also elaborate more on the process of managing patients that develop clinical opiate withdrawal symptoms.

Intervention period

Following randomization patients will be assigned to the MG or the NG group. For patients randomized to the MG a "non-formulary medication" order will be placed in the electronic medical record to alert nurses to follow the protocol for patients started on Methadone. For those in the NG group usual hospital protocol of weaning opioids will be followed.

The study is completed for each patient once extubated or discharged from ICU, death, comfort care measures, or after 30 days of participation in the study.

We will collect data regarding participants demographic characteristics, comorbidities, main admission diagnosis, use of mechanical ventilation and vasopressors, ICU and hospital LOS, ICU and hospital mortality. Vital signs, focused general examination, LFTs, with normal ICU standard of care will done. However, EKG will be done at baseline and on day 30 if patient is still on methadone. LFTs are only done at baseline. The duration of use of the medication is not expected to cause an increase in LFTs. The listed labs are the only additional labs other than what is usually ordered for standard care in ICU. The information will be collected by reviewing medical records and will be recorded in electronic form only, using REDCap.

#UTHealth Houston

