6. METHODS AND ASSESSMENTS

Based on the assumptions of successful extubation by day 5 of 50% of patients in the methadone group and 20% of patients in the control group and using a two tailed alpha level of 5%, a power of 80% our sample size calculation comparing proportions of two groups yielded 76. A 5% fallout as correction factor was 4 leaving us with a sample size of 80 patients. Statistical methods will include descriptive statistics and time to event analysis. Baseline characteristics will be reported. Data will be collected on a data collection sheet prior to transfer to REDCAPs database (Appendix 6). We will generate Kaplan-Meier curves and for comparison of hazard between groups we will use Cox regression (Cox proportional hazards model). Patients who die will be censored at time of death. Time of weaning will take into consideration only patients who were permanently disconnected from the ventilator. QTc values will be obtained from patient monitors and documented on data collection tool daily.

Randomization tables will be generated using REDCAPs database by study statistician. At the end of the study recorded information from REDCAPs will be exported to STATA for statistical analysis.

#UTHealth Houston

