6.1. Randomization and Blinding

Patients will be randomized between two groups, the Methadone group (MG) and the Non-Methadone group (NG). Randomization tables will be generated using REDCap database. Randomization will be stratified by Center of data collection. The investigators evaluating the primary and secondary outcomes will be blinded to the group assignments. The study participants, pharmacists, physicians and nurses taking care of the patients will not be blinded.

Assignment of patients to study groups will be by random allocation by randomization tables. There will be two randomization tables, one for Memorial Hermann Cypress and the other for Memorial Hermann Texas Medical Center. Patients predetermined to receive methadone will receive oral methadone which comes in 5mg tablets. Tablets will be crushed and administered via the feeding tube if patients are still on enteral feeding at the time the medication is administered. Patients predetermined not to receive methadone will continue treatment following usual care per hospital weaning protocols.

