10. SAMPLE SIZE AND STATISTICAL METHODS

10.1. Determination of Sample Size

Based on the assumptions of successful extubation by day 5 of 50% of patients in the methadone group and 20% of patients in the Non Methadone group and using a two tailed alpha level of 5%, a power of 80% our sample size calculation comparing proportions of two groups yielded 76. A 5% fall out as correction factor was 4 leaving us with a sample size of 80 patients.

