11. ETHICAL CONSIDERATIONS

11.1. Informed Consent

Consent will be obtained from legal authorized representatives while the patient in on mechanical ventilation and will be confirmed by the patient once extubated and sedation weaned in order for the patient to continue in the study. Consent forms and non-electronic data will be stored in protected locked storage in the office of the ICU Director while the research office will keep copies of the regulatory binders. A hospital translation phone will be used for communication with non-English speakers.

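### Unconditional replacement of dropouts, with patient consent confirmed only after extubation and no analysis-set rule, allows randomised patients to be swapped out for reasons linked to outcome or arm.

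*Combined protocol and SAP*

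**What the plan says.** - **Replacement (3.6):** "Subjects who drop out will be replaced". Dropout is not defined, and no reason, timing, arm or handling in the analysis is given.
- **Consent (11.1):** a representative consents during ventilation. That consent "will be confirmed by the patient once extubated and sedation weaned in order for the patient to continue in the study".
- **Primary outcome (2.5):** "Proportion of patients on methadone that get extubated by day number 5 from the date of intubation".
- **End of participation (4.2):** "The study is completed for each patient once extubated or discharged from ICU, death, comfort care measures, or after 30 days of participation".
- **Withdrawal (3.5):** the section deals with stopping the trial ("The study will be discontinued after completion or upon recommendation from Data Safety and Monitoring board"). It has no rule for an individual patient or for data already collected.
- **Blinding (6.1):** "The study participants, pharmacists, physicians and nurses taking care of the patients will not be blinded". Only the outcome evaluators are blinded.
- **Sample size (10.1):** 50% v 20%, two-sided 5%, 80% power gives 76 patients; then "A 5% fall out as correction factor was 4 leaving us with a sample size of 80 patients".
- **Analysis (6 and 10.2):** neither section defines an intention-to-treat or other analysis set, or a missing-data method. The nearest statement concerns the time-to-event analysis: "Time of weaning will take into consideration only patients who were permanently disconnected from the ventilator". It does not say who is counted in the day-5 proportion.

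**The concern.** To refuse at re-consent, a patient must first have been extubated. A patient who stays on the ventilator or dies on it cannot leave this way, so the exit depends on the event behind the primary outcome. Patients and staff know the allocation, so the refusal rate may also differ between arms. A replacement would ordinarily take over the dropout's place in the target of 80, and no sentence in the plan keeps the dropout in the analysis.

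If the replaced patients are not counted, the analysed groups are no longer the randomised groups. Enrolling more patients does not repair that. Refusal at equal rates would dilute a true effect; refusal at unequal rates could create or hide one.

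**Working it through.** **1. The plan's own figure.** For 50% v 20%, two-sided 5% and 80% power, the arcsine formula gives 37.9, so 38 per arm and 76 in total. The pooled normal formula gives 39 per arm (78). With the allowance, 76 / 0.95 = 80. The stated 76 and 80 reproduce. By exact enumeration of the Pearson chi-square test, power is 80.0% at 38 per arm and 81.7% at 40.

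**2. Model for refusal.** Let p be the true day-5 success rate, r the share of patients asked who refuse, and q the share of day-5 failures who are later extubated and asked. Failures and successes in the same arm are assumed to refuse at the same rate. If refusers are replaced and not counted, the retained success rate is

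p(1 − r) / (1 − r[p + (1 − p)q]).

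The documents give neither r nor q; both are assumptions here. Both 38 and 40 per arm are shown, because full replacement would bring the analysed number back to 40.

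**3. No true effect.** Take p = 35% in both arms (the midpoint of 50% and 20%), with refusal of 5% in methadone and 20% in control.

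- q = 0: 0.3325/0.9825 = 33.8% v 0.28/0.93 = 30.1%
- q = 0.5: 0.3325/0.96625 = 34.4% v 0.28/0.865 = 32.4%
- q = 1: 0.3325/0.95 = 35% v 0.28/0.80 = 35%

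| Failures asked (q) | False difference | Type I error, 38 per arm | Type I error, 40 per arm |
|---|---|---|---|
| 0 | 3.7 points | 6.5% | 6.2% |
| 0.5 | 2.0 points | 5.5% | 5.2% |
| 1 | 0 | 5.0% | 4.9% |

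Exchanging the two refusal rates reverses the sign and leaves the error rates unchanged. Equal refusal in both arms gives no bias when there is no true effect.

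**4. True effect of 50% v 20%, q = 0.**

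- Equal refusal of 10%: 0.45/0.95 = 47.4% v 0.18/0.98 = 18.4%. Power is 78.8% at 38 per arm and 80.1% at 40.
- Equal refusal of 20%: 0.40/0.90 = 44.4% v 0.16/0.96 = 16.7%. Power is 77.2% and 78.4%.
- Refusal of 20% in methadone only: 44.4% v 20%, a difference of 24.4 points.
- Refusal of 20% in control only: 50% v 16.7%, a difference of 33.3 points.

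The true 30-point difference can therefore be understated or overstated.

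**5. A further route, only if assumed.** Suppose a fraction d of methadone patients, all of them day-5 failures, were counted as dropouts and replaced, with none in control. The retained rate is p/(1 − d). With p = 35% in both arms, d = 10% gives 38.9% v 35% and d = 20% gives 43.8% v 35%. Type I error at 38 per arm is 6.3% and 11.9%.

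**The case against.** **Dropouts are not said to leave the analysis.** A reader might infer from 3.6 that they do, and hence that the comparison is biased. No section says so. Enrolling replacements while analysing everyone randomised would be compatible with the text. This stands: the documents support a risk, created by the replacement rule together with the missing analysis set.

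**The outcome is already recorded.** Section 4.2 ends each patient's study at extubation, so a day-5 success is known before consent is re-confirmed. Refusal might then affect only what follows. That weakens the re-consent route but does not close it, because 11.1 makes confirmation a condition of continuing and no section says that earlier data are kept. The consent form is not in the copy reviewed and may settle this.

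**Refusers need not be mostly successes.** It is tempting to assume that they are. Under the plan's 20% control rate, successes are the majority of extubated control patients only if 0.2/(0.2 + 0.8q) > 0.5, that is, q < 0.25. Follow-up runs to 30 days, so many failures may be extubated later and asked. The q = 0 row is the extreme case.

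**Stopping methadone is not called dropout.** The 6.3–11.9% errors need that classification, and the documents do not make it. The scenario shows only why the term needs a definition.

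**A 5% allowance together with replacement is not an arithmetic error.** This also stands. The allowance only shows that replacement is unnecessary for power.

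**Conclusion.** The concern holds as a risk to the randomised comparison. Replacement is unconditional, one exit opens only after extubation, care is open-label, and no analysis-set rule keeps a replaced patient in. Bias can run in either direction.

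Its size rests on refusal rates and on a share of failures asked that the documents do not give. In the worked null case the false difference runs from 3.7 points down to zero, and the re-consent route moves type I error only modestly. With equal refusal the loss of power is small. The documents do not support a claim that the primary result will be biased, nor the larger error rates, which need methadone stoppers to be counted as dropouts. The rule should still be changed, because replacement adds nothing that the sample size does not already provide.

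**What to change.** - **3.6:** delete the replacement rule. Define dropout, and state that stopping methadone is not dropout from the analysis.
- **6 and 10.2:** state that every randomised patient is analysed in the assigned arm.
- **3.5 and 11.1:** keep the day-5 outcome recorded up to extubation when a patient declines to continue, as far as the consent form and IRB allow. Where it cannot be kept, treat it as missing, with a sensitivity analysis over the missing outcomes. Report refusals by arm.
- **4.2 and 11.1:** reconcile completion of the study at extubation with consent needed to continue after it.
- **10.1:** keep 80 patients with the 5% allowance. Power is about 81.7% with all 80 analysed and about 80% with 76.

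The cost is protocol wording and possibly a sentence in the consent form on data already collected, which must be checked against the form. The sample size does not change. If the IRB requires a refuser's data to be deleted, some outcomes will be missing.

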4.1 Allocation

All patients admitted to the medical ICU will be screened for eligibility. Group assignment will be done using the randomization module of the Research Electronic Data Capture (REDCap) platform. Patients will be randomized in a 1 to 1 ratio, using permuted blocks of 4 or 6, into one of two groups: methadone group and the Non-Methadone group. The randomization will be stratified based on location where patients will be recruited.

4.2 Interventions

Pre-intervention period (1 month)

The objective of this period is to standardize the process to improve familiarity to the investigators. Study procedures will be presented to the nurses by oral presentations, printed material, and by email. The information will include detailed explanation of the process of tapering methadone and weaning patients off opiates as stipulated in the study. It will also elaborate more on the process of managing patients that develop clinical opiate withdrawal symptoms.

Intervention period

Following randomization patients will be assigned to the MG or the NG group. For patients randomized to the MG a "non-formulary medication" order will be placed in the electronic medical record to alert nurses to follow the protocol for patients started on Methadone. For those in the NG group usual hospital protocol of weaning opioids will be followed.

The study is completed for each patient once extubated or discharged from ICU, death, comfort care measures, or after 30 days of participation in the study.

We will collect data regarding participants demographic characteristics, comorbidities, main admission diagnosis, use of mechanical ventilation and vasopressors, ICU and hospital LOS, ICU and hospital mortality. Vital signs, focused general examination, LFTs, with normal ICU standard of care will done. However, EKG will be done at baseline and on day 30 if patient is still on methadone. LFTs are only done at baseline. The duration of use of the medication is not expected to cause an increase in LFTs. The listed labs are the only additional labs other than what is usually ordered for standard care in ICU. The information will be collected by reviewing medical records and will be recorded in electronic form only, using REDCap.

#UTHealth Houston

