2.3. Secondary Objectives

To assess the safety of methadone administration in critically ill patients while in the hospital.

To determine hospital length of stay from the time of enrollment to the time of discharge

2.4. Potential Risks and Benefits:

a. End Points – Efficacy

The study might show the efficacy and potency of methadone in decreasing the length of stay in ICU and duration of mechanically intubation in critically ill patients.

b. End Points - Safety

Adverse events that could be anticipated during the study include signs of opioid withdrawal, elevated liver enzymes, ileus, hypotension and QTC prolongation. Adverse events will be reported in the adverse events registry.

The only two adult studies reported on the use of methadone to wean opioids on mechanical ventilation showed that the much-anticipated risk of QTC prolongation was similar in both patients who received methadone and those that did not receive methadone as shown in the study by Wanzuita et al and Al-Qadheeb et al. [5] Methadone was well tolerated in both studies.

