8. SAFETY MEASUREMENTS

Any adverse events encountered will be documented in the patients' chart once it is noted. These include QTc >500, high grade arrhythmias such as ventricular tachycardia, hypotension and elevated Liver function testing more than 2.5 times the upper limit of normal.

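### Liver-test elevation is a named adverse event, but no liver test is scheduled after baseline and the data sheet has no field for one, so any count would rest on routine tests with an unknown denominator

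*Combined protocol and SAP*

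**What the plan says.** Three sections and one appendix bear on this.

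- Section 2.4, under the safety end points, gives the events that could be anticipated as "signs of opioid withdrawal, elevated liver enzymes, ileus, hypotension and QTC prolongation".
- Section 8 names among the adverse events to be documented "elevated Liver function testing more than 2.5 times the upper limit of normal". On how events are recorded it says "Any adverse events encountered will be documented in the patients' chart once it is noted".
- Section 4.2 says "LFTs are only done at baseline" and gives the reason: "The duration of use of the medication is not expected to cause an increase in LFTs". The same paragraph also says "Vital signs, focused general examination, LFTs, with normal ICU standard of care will done", then "The listed labs are the only additional labs other than what is usually ordered for standard care in ICU", and on the data source "The information will be collected by reviewing medical records".
- Appendix 6, the data collection sheet, has one general line for adverse events and a line for QTc, but no line for liver tests.

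Methadone's safety is a secondary objective (section 2.3). The secondary outcomes in section 2.5 include QTc prolongation and no liver outcome. Section 10.2 says that no safety analysis will be done. Treating physicians and nurses are not blinded (sections 6.1 and 7.5).

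**The concern.** The only liver test that the study itself requires comes before treatment. It can show an abnormality already present but not one that develops later. The section 8 threshold is also not tied to the baseline value. Section 3.4 excludes end-stage liver disease by INR and bilirubin, not by enzymes, so a patient could enter the trial already above the threshold.

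What is at stake is how a liver-event count would be read by the quarterly adverse-event review and the DSMB, and in any account of the safety objective. A low count could mean little harm or little testing, and the plan collects nothing that would separate the two. Staff who order tests know the arm, so testing could also differ between arms.

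**Working it through.** The documents state no liver-event rate and no testing frequency, so there is no figure of the plan's own to reproduce. The check compares the passages and then illustrates the size under stated assumptions.

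**1. Can the planned data show a treatment-emergent rise?**

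| Step needed | What the plan provides |
|---|---|
| Event defined | Yes, above 2.5 × ULN (section 8), with no reference to baseline |
| Study test after baseline | None (section 4.2) |
| Test in routine care | Mentioned in section 4.2; timing and frequency not stated |
| Value and date recorded | No liver-test field in Appendix 6 |
| Number of patients tested | Not collected |
| Event recorded | When someone notices it (section 8) |

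QTc is a useful contrast: section 6 has it documented daily, and it has its own line in Appendix 6. Section 4.2 also plans an EKG at day 30 for patients still on methadone. The plan thus foresees exposure of up to 30 days, while giving duration of use as the reason for no later liver test.

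**2. What would zero events mean?**

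Input: 80 patients at 1:1 (sections 10.1 and 4.1), so 80 / 2 = 40 per arm. The one-sided 95% upper bound with zero events among n tested patients is 1 − 0.05^(1/n). The values 20 and 10 are assumptions.

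- n = 40: 1 − 0.05^(1/40) = 7.2%
- n = 20: 1 − 0.05^(1/20) = 13.9%
- n = 10: 1 − 0.05^(1/10) = 25.9%
- n = 0: no bound

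The 7.2% is due to sample size alone. The part due to ascertainment is the move from 7.2% to the larger figures, and the plan does not collect the n that would say which applies.

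**3. How far could the count fall short?**

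Observed rate = true rate × probability of a later test that would show the rise. With an assumed true rate of 10% and 40 patients per arm:

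| Assumed testing probability | Observed rate | Expected cases per arm | Chance of at least one case |
|---|---|---|---|
| 25% | 2.5% | 1 | 64% |
| 50% | 5% | 2 | 87% |
| 75% | 7.5% | 3 | 96% |
| 100% | 10% | 4 | 99% |

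For true rates of 5% and 20%, the observed rate runs from 1.25% to 5% and from 5% to 20% over the same range of testing.

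**4. Could testing alone create a difference?**

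Assume a true rate of 10% in both arms, with 80% tested in one arm and 40% in the other.

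- Tested: 40 × 0.8 = 32 and 40 × 0.4 = 16.
- Expected events found: 32 × 0.10 = 3.2 and 16 × 0.10 = 1.6.
- Over all randomized: 3.2 / 40 = 8% against 1.6 / 40 = 4%.
- Over those tested: 3.2 / 32 = 10% against 1.6 / 16 = 10%.

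Knowing the number tested removes the spurious difference here, provided that testing is unrelated to the patient's true risk.

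**The case against.** The strongest reply is that section 4.2 must be read as a whole. It mentions liver tests alongside routine ICU care, describes the study labs as additional to what is usually ordered, and draws its data from the medical record. On that reading only the study-specific test is confined to baseline, and routine tests continue and can be reviewed. This is a fair reading. A reader might infer from the baseline-only sentence that a later rise cannot be detected at all, or that any reported rate would be meaningless. The documents do not support that: a care-ordered test can reveal a rise, and the general adverse-event line can hold it. What the reading does not supply is a testing frequency, a place for the values or a count of those tested.

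Second, no liver-event rate or comparison between arms is planned: section 2.5 has no liver outcome and section 10.2 rules out a safety analysis. This stands, and it limits the point to counts that reach the adverse-event registry, the quarterly review or a report on the safety objective. It is also tempting to say that methadone patients will be tested more. Nothing in the documents says so; unblinded care only makes unequal testing possible.

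Third, the choice is reasoned. The plan gives its ground for no later test, and listing an event as one that could occur does not oblige a trial to schedule a test for it. That is so, but section 8 goes beyond a list by setting a numeric threshold, which can be applied only where a later value exists.

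**Conclusion.** The point holds in a limited form. Sections 2.4 and 8 treat liver-test elevation as an event to be found, while section 4.2 schedules no test that could find it after treatment starts and Appendix 6 gives it no field. Detection depends on care-ordered tests of unstated frequency. A count would probably be under-ascertained, would have no denominator, and could differ between arms because of testing.

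The true size is unknown. The bounds of 7.2%, 13.9% and 25.9%, and the 8% against 4% contrast, are illustrations that rest on assumed numbers tested and, for the contrast, an assumed true rate. If every patient has regular liver tests in routine care and staff act on them, the shortfall could be small; the plan as written would not show whether that was the case. The issue is minor: it does not touch the primary outcome, and it is cheap to repair.

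**What to change.** 1. Reconcile sections 2.4, 4.2 and 8. In section 4.2, say whether the baseline-only sentence refers to the study-specific test, and how liver tests from routine care are used.
2. Add to section 4.2 and Appendix 6 that every post-baseline liver-test value obtained in routine ICU care is abstracted, with its date, in both arms, next to the baseline value.
3. Report treatment-emergent elevations, judged against the baseline value, among patients with at least one later value, and give the number tested per arm. If tests are ordered on suspicion, the tested patients are a selected group. The denominator makes this visible but does not remove it, and the report should say so.

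Taking the event out of section 8 would not help: section 2.4 would still list it, and ascertainment would be no better. Whether to schedule further tests is for the investigators.

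The cost is a little more chart review and a few added fields. No extra blood test is needed.
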